8.3.3 Causality Collection

The investigator should assess causal relationship between IMP and each AE and answer ‘yes’ or ‘no’ to the question ‘Do you consider that there is a reasonable possibility that the event may have been caused by the IMP?’

For SAEs causal relationship should also be assessed for other medication and study procedures. Note that for SAEs that could be associated with any study procedure the causal relationship is implied as ‘yes’.

A guide to the interpretation of the causality question is found in [Appendix B](#) to the Clinical Study Protocol.

8.3.4 Adverse Events Based on Signs and Symptoms

All AEs spontaneously reported by the participant or reported in response to the open question from the study site staff: Have you had any health problems since the previous visit/you were last asked?, or revealed by observation, will be collected and recorded in the eCRF. When collecting AEs, the recording of diagnoses is preferred (when possible) to recording a list of signs and symptoms. However, if a diagnosis is known and there are other signs or symptoms that are not generally part of the diagnosis, the diagnosis and each sign or symptom will be recorded separately.

8.3.5 Adverse Events Based on Examinations and Tests

The results from the CSP mandated laboratory tests and vital signs will be summarised in the CSR.

Deterioration as compared to baseline in protocol-mandated laboratory values and vital signs should therefore only be reported as AEs if they fulfil any of the SAE criteria, are the reason for discontinuation of treatment with the investigational product or are considered to be clinically relevant as judged by the investigator (which may include but not limited to consideration as to whether treatment or non-planned visits were required or other action was taken with the study intervention, eg, dose adjustment or drug interruption).

If deterioration in a laboratory value/vital sign is associated with clinical signs and symptoms, the sign or symptom will be reported as an AE and the associated laboratory result/vital sign will be considered as additional information. Wherever possible the reporting investigator uses the clinical, rather than the laboratory term (eg, anaemia versus low haemoglobin value). In the absence of clinical signs or symptoms, clinically relevant deteriorations in non-mandated parameters should be reported as AE(s).

Any finding from physical examination (including neurological examination) should be evaluated as normal/abnormal. If the abnormal physical finding (including neurological examination) started prior to enrolment, it must be recorded as medical history. If the abnormal physical finding (including neurological examination) started or worsened after

enrolment, it must be recorded as an Adverse Event.

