Visit 2 (randomisation): At Visit 2, participants are required to be fasting for at least 8 hours overnight prior to the visit; participants are permitted to drink water during this period until 1 hour before blood sampling. Eligibility criteria must be verified by checking screening laboratory assessments and inclusion/exclusion criteria. CCI [REDACTED]

[REDACTED] A complete physical examination, neurologic examination and vital sign assessments will be performed. Blood samples, including those needed for efficacy and pharmacodynamics, ADA and urine samples will be obtained in accordance with the SoA. ECG will be checked. If the participant fulfils all inclusion criteria and none of the exclusion criteria, the participant will be randomised in IRT/ RTSM and IMP will be administered as a SC injection. Post-dose assessments (complement activation profile and coagulation parameters) will take place 2 -hours after dosing of IMP.

Visit 3: At Visit 3, concomitant medications, AEs, and an assessment for ISRs will be reviewed, as well as an abbreviated physical exam and assessment of vital signs. Blood and urine samples, and platelet count, will be obtained in accordance to the SoA.

Dosing Visits (Visits 4, 6, 8, 10, 12, 14): At dosing visits, participants are required to be fasting for at least 8 hours overnight prior to the visit; participants are permitted to drink water during this period until 1 hour before blood sampling. Concomitant medications, AEs and an assessment for ISRs will be reviewed. An abbreviated physical exam a neurologic examination and assessment of vital signs will be performed. Review of the most recent platelet count within 14 (+/-3 days) prior to the visit. ECG, blood samples, including those needed for efficacy and pharmacodynamics, and urine samples will be collected in accordance with the SoA. Blood samples for ADA will be collected. PK samples will be collected pre-dose on Visits 4, 8, and 12. Study intervention will then be administered. Post-dose assessments (coagulation panel and complement activation profile; PK at Visit 12) will be obtained 2 hours after dosing of IMP.

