8.3.1 Time Period and Frequency for Collecting AE and SAE Information

AEs will be collected from randomisation, (Visit 2) and SAEs from signing the ICF (Visit 1). Both AEs and SAEs will continue to be collected throughout the treatment period and including the follow-up period (Visit 18).

If the investigator becomes aware of an serious adverse event with a suspected causal relationship to the IMP that occurs after the end of the clinical study in a participant treated by him or her, the investigator shall, without undue delay, report the SAE to the sponsor.

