8.3.2 Follow-up of AEs and SAEs

Any AEs that are unresolved at the participant's last AE assessment in the study are followed up by the investigator for as long as medically indicated, but without further recording in the eCRF. AstraZeneca retains the right to request additional information for any participant with ongoing AE(s)/SAE(s) at the end of the study, if judged necessary.

Adverse event variables

The following variables will be collected for each AE:

- AE (verbatim)
- The date when the AE started and stopped
- Maximum intensity (mild, moderate, severe)
- Whether the AE is serious or not
- Whether the AE required treatment
- Whether the AE was assessed as an ISR
- Investigator causality rating against the IMP(s) (yes or no)
- Action taken with regard to IMP(s)
- Outcome

In addition, the following variables will be collected for SAEs:

- Date AE met criteria for SAE
- Date investigator became aware of SAE
- AE is serious due to
- Date of hospitalisation
- Date of discharge
- Probable cause of death if applicable
- Date of death
- Autopsy performed
- Causality assessment in relation to study procedure(s)
- Causality assessment in relation to other medication

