9.3 Populations for Analyses

For purposes of analysis, the following populations are defined:

Table 7 Populations for Analysis

Population/Analysis set	Description
Enrolled	All participants who sign the ICF
Full Analysis Set (FAS)	All participants who were randomly assigned to study intervention. Data from participants will be analysed according to the treatment to which they were randomly assigned.
Safety analysis set (SAS)	The Safety analysis set consists of all participants who have received at least one dose of investigational product. Erroneously treated participants (eg, those randomised to treatment A but actually given treatment B) are accounted for in the treatment group of the treatment they actually received. A participant who has on one or several occasions received active IMP is classified as active and is accounted for the active IMP treatment group.
PK Analysis Set	The PK analysis set will consist of all subjects who receive at least 1 dose of AZD8233, for whom at least 1 post-dose PK concentration assessment is available as determined at the final protocol deviations meeting prior to unblinding of this study. Subjects will be presented in accordance to the actual treatment received.

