9.4.3.1 Primary Endpoint(s)

Adverse Events

Safety variables will be summarised by treatment group and visit using descriptive statistics (n, mean, SD, median, minimum and maximum [and geometric mean and coefficient of variation, if applicable]) for continuous data and absolute and relative frequencies for categorical data.

Clinical laboratory data and ECG parameters will be summarised by treatment group and visit.

Adverse events will be summarised by PT and SOC using MedDRA vocabulary. Adverse events that led to discontinuation of IMP, SAEs, AEs by severity and causally related AEs will also be presented. All AE summaries will be done by treatment group. Adverse events will be coded using the most recent version of MedDRA that will have been released for execution at AZ.

AEs will be presented for each treatment group by SOC, PT covering number and percentage of participants reporting at least one event and number of events where appropriate.

An overview of AEs will present for each treatment group the number and percentage of participants with any AE, AEs with outcome of death, serious AEs, and AEs leading to discontinuation of IMP, as well as AEs leading to IMP interruptions.

AEs of ISRs will be summarised separately.

Separate AE tables will be provided taking into consideration relationship to IMP as assessed by the investigator, seriousness, death and events leading to discontinuation of IMP and other significant adverse events and timing of events.

An additional table will present number and percentage of participants with most common AEs. Most common (eg, frequency \geq x%) will be defined in the SAP.

In accordance with the requirements of the FDA, a separate table will present non-serious AEs occurring in more than 5% of participants in any treatment group.

Key participant information will be presented for participants with AEs with outcome of death, serious AEs, and AEs leading to discontinuation of IMP.

An AE listing for the safety analysis set will cover details for each individual AE; an AE listing for participants who were not exposed to IMP is presented separately.

Full details of AE analyses will be provided in the SAP.

AEs occurring prior to start of IMP and treatment emergent AEs will be presented separately.

Treatment emergent

The following events are considered treatment emergent:

- Adverse events with an onset date on or after first dose of IMP
- Worsening of pre-existing events on or after first dose of IMP

Vital signs

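### Sections 8.3.1 and 8.3.5 start recording of non-serious examination findings at different points, and date-only onset lets pre-dose Day 1 findings count as treatment emergent

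*Protocol*

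**What the plan says.** - **Which examination findings are AEs (Section 8.3.5).** A finding that "started prior to enrolment, it must be recorded as medical history". The other branch reads "If the abnormal physical finding (including neurological examination) started or worsened after" enrolment, and such a finding has to be recorded as an AE. Table 7 in Section 9.3 describes the enrolled population as "All participants who sign the ICF", which happens at Visit 1.
- **When AEs are collected (Section 8.3.1).** "AEs will be collected from randomisation, (Visit 2) and SAEs from signing the ICF (Visit 1"). The Schedule of Activities agrees: the AE review at screening is limited to SAEs.
- **What is recorded (Section 8.3.2).** Timing is "The date when the AE started and stopped". The list contains no clock time and no marker of onset before or after a dose. The summary of changes shows that time was removed from these variables deliberately.
- **Visit 2 (Section 8, General Description of Study Visits).** "A complete physical examination, neurologic examination and vital sign assessments will be performed". Randomisation and the first dose follow at the same visit.
- **Analysis (Section 9.4.3.1).** Treatment emergent covers "Adverse events with an onset date on or after first dose of IMP", plus worsening of pre-existing events from that point. The same section states: "AEs occurring prior to start of IMP and treatment emergent AEs will be presented separately".

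**The concern.** There are two linked problems. First, two sections give sites different start points for the same kind of record, so a non-serious finding arising between consent and randomisation is mandatory under one and outside collection under the other. Sites may resolve this differently, and about 100 are planned. Second, one calendar date holds both the last pre-treatment examination and the first dose, while the AE record and the treatment-emergent rule work at the level of the date. Safety and tolerability is a primary objective and AEs are one of its measures, so it matters which findings enter the treatment-emergent tables and which belong to baseline.

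**Working it through.** No power, alpha or sample-size figure is involved, and the plan states no number to reproduce. The check sets the passages side by side.

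**Step 1: the gap between the start points.** The Schedule of Activities places Visit 1 at Day -28 to Day -1 and Visit 2 at Day 1. The gap is therefore up to 28 days, plus the part of Day 1 before randomisation.

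**Step 2: the order within Day 1.** Section 8 lists the sequence as ECG; then vital signs, physical and neurological examination and AE review; then samples; then dosing. It also places random assignment at Visit 2 after the assessments and sampling. The examinations therefore precede both randomisation and the first dose, on the same date.

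**Step 3: classify a non-serious finding by onset.** The first three rows can be findings seen at the pre-dose Visit 2 examination. The fourth is a genuine post-dose event, for comparison.

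| Onset | Section 8.3.5 | Section 8.3.1 and Schedule of Activities | Section 9.4.3.1 |
|---|---|---|---|
| Before enrolment | Medical history | Not an AE | Not treatment emergent unless it worsens on or after first dose |
| After enrolment, up to Day -1 | AE | Outside collection | If recorded, pre-treatment by date |
| Day 1, before the dose | AE | Before randomisation, though at the visit where collection starts | Onset date equals first-dose date, so treatment emergent |
| Day 1, after the dose | AE | Collected | Treatment emergent, correctly |

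The contradiction lies in the second row and, read strictly, in the third. The misclassification lies only in the third. The third and fourth rows carry the same onset date, and no timing field listed in Section 8.3.2 tells them apart. That is why the split between pre-treatment and treatment-emergent events fails for non-serious events with Day 1 onset.

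**Step 4: compare with the baseline rule.** For safety-set analyses, Section 9.4.1 takes as baseline the last non-missing value up to and including the date of the first dose. Measurements from the pre-dose Visit 2 session thus count as baseline, while an examination finding from the same session can count as treatment emergent.

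**Step 5: size.** Let p be the share of each arm with a pre-dose finding dated Day 1. The extra treatment-emergent participants per arm number 188 × p (188 per arm, Section 9.2). The protocol gives no value for p. Purely as an assumption, p of 2% to 5% gives 188 × 0.02 = 3.8 to 188 × 0.05 = 9.4 per arm. Take an assumed true contrast of 4% against 1%, ignore overlap, and put every such finding under the same tabulated term:

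- difference: 4 − 1 = 3 points; (4 + 2) − (1 + 2) = 3; (4 + 5) − (1 + 5) = 3
- ratio: 4/1 = 4.0; 6/3 = 2.0; 9/6 = 1.5

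The difference does not move; only the ratio shrinks. This shows the direction of the effect and is not an estimate of its size.

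**The case against.** A reader might infer that every abnormality found at the Visit 2 examination ends up in the treatment-emergent tables, for example unrecorded neuropathy in a participant with diabetes. The protocol does not support this. Section 8.3.5 turns on when a finding started, not when it was seen, so long-standing neuropathy is medical history. A finding dated after consent but before Day 1 separates by date. No passage tells sites to enter the detection date as onset, although a site might do so for a sign without symptoms.

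A reader might also infer that no neurological examination exists at enrolment to compare with. Section 8.2.1 includes the neurological system in the complete physical examination, which is done at screening. Only the dedicated neurological examination starts at Visit 2.

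Other points on this side also have force. On a strict reading of Section 8.3.1, a non-serious finding seen before randomisation would not be collected as an AE, so the misclassification requires a site to follow Section 8.3.5. The separate presentation of pre-treatment AEs still works for SAEs dated before Day 1, which are collected from consent. AEs are tabulated by preferred term and system organ class, so any excess would spread over several terms. Safety is descriptive and no AE ratio is planned.

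Finally, the SAP is not at hand and may hold a same-day convention. It could assign all Day 1 events to one side, but it could not recover an order that the listed AE variables do not hold. Nor can it settle what sites enter, which the protocol governs.

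These points limit the reach of the problem. They do not remove the conflict between 8.3.5 and 8.3.1, or the ambiguity of Day 1 onset.

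**Conclusion.** The point holds in a limited form. The start points in Sections 8.3.5 and 8.3.1 (with the Schedule of Activities) are incompatible for non-serious findings arising between Visit 1 and randomisation. Separately, a pre-dose finding given a Day 1 onset date can be counted as treatment emergent.

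The second part rests on two assumptions: that sites record such a finding as an AE, and that they date it Day 1. The number affected cannot be derived from the protocol. Because the examination precedes randomisation and the study is double blind, the effect should be similar in both arms: it would inflate counts and blur a relative contrast, and it gives no reason to expect bias towards either arm. It should be corrected because it decides which events enter the primary safety tables and cannot be repaired from the listed AE variables afterwards.

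**What to change.** 1. Use one start point in Section 8.3.1, Section 8.3.5 and the Schedule of Activities. For example, record non-serious abnormalities present at the pre-dose Visit 2 examination as medical history or baseline findings, and record those new or worse afterwards as AEs. Leave SAE collection from consent unchanged.
2. Add to the AE variables in Section 8.3.2 an indicator, for AEs with Day 1 onset only, of whether onset was before or after the first dose.
3. In Section 9.4.3.1, use that indicator to decide treatment emergence for Day 1 events, so that the separate presentation of pre-treatment AEs can be produced.

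The cost is aligned wording in these places and one extra eCRF field for Day 1 events. No visit or procedure is added.

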8.3.6 Hy's Law

Cases where a participant shows elevations in liver biochemistry may require further evaluation and occurrences of AST or ALT $\geq 3 \times$ ULN together with TBL $\geq 2 \times$ ULN may need to be reported as SAEs. Please refer to [Appendix E](#) for further instruction on cases of increases in liver biochemistry and evaluation of Hy's Law

8.3.7 Reporting of Serious Adverse Events

All SAEs have to be reported, whether or not considered causally related to the investigational product, or to the study procedure(s). All SAEs will be recorded in the eCRF.

If any SAE occurs in the course of the study, investigators or other site personnel will inform the appropriate AstraZeneca representatives within one day ie, immediately but **no later than 24 hours** of when he or she becomes aware of it.

The designated AstraZeneca representative will work with the investigator to ensure that all the necessary information is provided to the AstraZeneca Patient Safety data entry site **within one calendar day** of initial receipt for fatal and life-threatening events **and within five calendar days** of initial receipt for all other SAEs.

For fatal or life-threatening AEs where important or relevant information is missing, active follow-up will be undertaken immediately. Investigators or other site personnel will inform AstraZeneca representatives of any follow-up information on a previously reported SAE within one calendar day, ie, immediately but **no later than 24 hours** of when he or she becomes aware of it.

Once the investigators or other site personnel indicate an AE is serious in the EDC system, an automated email alert is sent to the designated AstraZeneca representative.

If the EDC system is not available, then the investigator or other study site staff reports an SAE to the appropriate AstraZeneca representative by telephone.

The AstraZeneca representative will advise the investigator/study site staff how to proceed.

Investigators or other site personnel send relevant CRF modules by fax (PPD [redacted]) or email (PPD [redacted]) to AstraZeneca Patient Safety Data Entry Site, Tata Consultancy Services.

The reference document for definition of expectedness/listedness is the IB for AZD8233.

8.3.8 Pregnancy

All pregnancies and outcomes of pregnancy should be reported to AstraZeneca except for:

- If the pregnancy is discovered before the study participant has received any study intervention

Pregnancy itself is not regarded as an adverse event unless there is a suspicion that the investigational product under study may have interfered with the effectiveness of a contraceptive medication. Congenital anomalies/birth defects and spontaneous miscarriages should be reported and handled as SAEs. Elective abortions without complications should not be handled as AEs. The outcome of all pregnancies (spontaneous miscarriage, elective termination, ectopic pregnancy, normal birth or congenital anomaly) should be followed up and documented even if the participant was discontinued from the study.

If any pregnancy occurs in the course of the study, then the investigator or other site personnel informs the appropriate AstraZeneca representatives within **one day**, ie, immediately but **no later than 24 hours** of when he or she becomes aware of it.

The designated AstraZeneca representative works with the investigator to ensure that all relevant information is provided to the AstraZeneca Patient Safety data entry site **within one or five calendar days** for SAEs (see Section 8.3.7) and **within 30 days** for all other pregnancies.

The same timelines apply when outcome information is available.

The pregnancy report module in the eCRF is used to report the pregnancy and the paper-based pregnancy outcome module is used to report the outcome of the pregnancy.

8.3.8.1 Paternal Exposure

Male participants should refrain from fathering a child during the study and for 3 months following the final follow-up visit (see also Section 5.3.3).

In case of pregnancy of the partner of a male participants, the partner's pregnancy should be reported on the pregnancy form (consent from the partner must be obtained before the pregnancy form is completed) following the same timeframe and routing as described for any participant's pregnancy. Pregnancy of the participant's partner is not considered to be an AE. These pregnancies will also be followed up, and the outcome of the pregnancy (spontaneous miscarriage, elective termination, ectopic pregnancy, normal birth or congenital anomaly) should, if possible, be obtained and documented.

8.3.9 Medication Error

If a medication error occurs in the course of the study, then the investigator or other site personnel informs the appropriate AstraZeneca representatives within **1 day**, ie, immediately but **no later than 24 hours** of when he or she becomes aware of it, and records the error on the Medication error eCRF module.

The designated AstraZeneca representative works with the investigator to ensure that all relevant information is completed within **one** (Initial Fatal/Life-Threatening or follow up

Fatal/Life-Threatening) **or five** (other serious initial and follow up) **calendar days** if there is an SAE associated with the medication error (see Section 8.3.7) and **within 30 days** for all other medication errors.

The definition of a Medication Error can be found in Appendix B 4.

